## 4.3 Subject Recruitment and Screening

A screening period and observation that subject's clinical status is stable and requiring substantial oxygen support will be observed for 48 hours. Research team will be informed of subjects meeting eligibility criteria and plan to approach. A member of the subject's clinical care team will first approach an individual subject or LAR who is a potential candidate for participation. If the subject or LAR is interested in participating in the study, a study team member will explain the purpose, procedures, and intent of the study to each potential study subjects or LAR. Written informed consent must be obtained before the subject can begin any screening procedures that are not considered standard patient care.

In the event a legal representative provides consent at the time of enrollment, the subject's diminished capacity will be assessed throughout study enrollment, and they will be approached for consent if/when they regain the ability to make medical decisions for themselves.

Subjects will not be compensated for participating in the study.

## 4.4 Early Withdrawal of Subjects

### 4.4.1 When and How to Withdraw Subjects.

Study completion is at the end of 2 day wash out period defined by 2 days after the last administration of Voxelotor. If a patient withdraws informed consent, the patient will be withdrawn from Voxelotor study treatments and all study related assessments.

A patient will be withdrawn from the study treatment if any of the events listed below occur but should continue to be followed according to the intervention table:

- Decision by the Investigator that it is not in the best interest of a patient to continue treatment.
- Subjects are free to withdraw their consent at any time; the PI will withdraw a subject if any adverse response is thought to be due to Voxelotor.
- If a patient receives a "go call" for solid organ lung transplant then study medication will be discontinued and the subject will proceed to the study wash out phase, as the PK and PD of Voxelotor in the setting of surgery, blood loss, and blood transfusion is unknown. Voxelotor is oral administration only and the effect of blood transfusion "diluting" the Voxelotor modified RBCs is unknown, so the effect of Voxelotor in this setting will be confounded by the common scenario of blood transfusion and/or hemodilution. Also, the indication for Voxelotor, to maintain SaO2 in the face of a significant Alveolar-arterial pO2 gradient, will have passed with the implantation of donor lungs.
- If a patient suffers bleeding complications requiring blood transfusion, as the PK and PD of Voxelotor in the setting of blood loss and blood transfusion is unknown. The effect of blood transfusion "diluting" the Voxelotor modified RBCs is unknown, so the effect of Voxelotor in this setting will be confounded and they will enter the wash-out period.
- As Voxelotor increases the binding of oxygen to hemoglobin (providing the treatment effect of increased SpO2 for a given pO2), we will monitor for the possibility of inadequate oxygen being off-loaded to the tissues by tracking venous blood gases for evidence of metabolic acidosis from tissue beds and tracking renal function as a reflection of adequacy of tissue oxygen during administration of Voxelotor.

To provide a complete safety review of each patient, participants will be enrolled and end study participation before the next subject is enrolled. This will be done for the first five participants. For the remaining 15 participants, when an SAE occurs with a subject, enrollment of new participants will pause until the SAE is completely reviewed by the PI. After three unexpected, related SAEs are reported in this study, the enrollment of new participants will be halted.

# 4.4.2 Data Collection and Follow-up for Withdrawn Subjects

Patients enrolled in this study will receive 5 days of Voxelotor treatment, in the perioperative setting of lung transplantation for some subjects. In the event a patient receives a lung transplant during the 5-day treatment period, follow-up of survival status will continue through the 2 day wash out period post-transplant. Many confounding reasons related to the complexity of the recovery and the complication profile of lung transplantation render further follow-up unrealistic beyond the duration that subjects receive Voxelotor, as supported by few safety concerns despite administration to many patients with significant co-morbidities.

# 5 Study Drug

## 5.1 Description

Voxelotor (GBT440) is a small molecule inhibitor of HbS polymerization which allosterically modifies Hb-O2 affinity.

Voxelotor is a white-to-yellow-to-beige compound in crystalline Form II of GBT440 free base. It is non-hygroscopic. It is highly soluble in common organic solvents such as acetone and toluene and insoluble in water (approximately 0.03 mg/mL). Voxelotor drug substance is manufactured in accordance with GMP. The chemistry used in the production of Voxelotor drug substance is well established. The manufacturing process uses equipment commonly available in the industry.

Voxelotor will be supplied as 500 mg tablets, or as 100 mg and 300 mg dispersible tablets for a total daily dose of 1000 mg per day, which may be increased to a total maximum dose of 1500 mg per day if subject tolerates initial dose as determined per PI.

## 5.2 Treatment Regimen

All participants will receive Voxelotor, administered orally as approved tablets or dispersible tablets for the duration of their enrollment in the study. Subjects will be dosed orally or given via feeding tube (when indicated). Voxelotor in all formulations, may be taken with or without food. Voxelotor dispersible tablets should be dispersed in clear liquid (e.g., water, apple juice).

If the dispersible tablets are given, the instructions for preparation prior to administration are as follows:

Table 3: Volume of Liquid per Dose of Voxelotor Dispersible Tablet

Voxelotor Dispersible Tablet Dose (mg)	Volume of Water (cc)		
400 to 600	No less than	5	
700 to 900	No less than	7.5	
1000 to 1200	No less than	10	
1500	No less than	12.5	

Note: one cubic centimeter (cc) is equivalent to one milliliter (mL)

500 mg of voxelotor will be administered two times daily (for a total daily dose of 1000 mg per day) for 5 days. This dose may increase to a total maximum daily dose of 1500 mg (500 mg three times a day) if subject tolerates initial dose as determined by PI. In the event the voxelotor administration needs to be discontinued for patient safety reasons during one of the study administration days, further doses of voxelotor will be discontinued and the protocol will progress to the wash out phase identified in the schedule of activities (Table 2).

# 5.3 Method for Assigning Subjects to Treatment Groups

This is an open label single arm study. Subjects will not be randomized.

## 5.4 Preparation and Administration of Study Drug

Voxelotor will be dispensed from IDS Pharmacy. Drug will be picked up by research team member and delivered to patient's nurse.

## 5.5 Subject Compliance Monitoring

Voxelotor drug product must be administered orally daily. If a participant misses a dose, the participant should resume normal dosing next day (i.e., the dose on the day after a day of a missed dose should not be increased or decreased).

The subjects will inpatient, and medications will be administered by the RN and noted in the record as given/not given. If study PI plans to dose modify/hold for AEs that affect safety and tolerability, a trial of reducing or holding (temporarily stopping) the dose may be used. In prior sickle cell disease (SCD) studies, modification of dose (or dosage hold) was utilized based upon the exact event and the grade of the event. Dose was reduced for Grade 2 AE and subject reassessed, Dose was held or discontinued (for SAE) for Grade 3, as determined by PI.

Table 4. Dose Modification Guidelines for Study Drug Related Adverse Events

Dose Reduction					
Event	Recommended Action				
Grade ≥ 2 (NCI grading scale) AE deemed considered related to study drug by the Investigator AND Precludes continued dosing at the current dose level due to safety concern or lack of tolerability (in the Investigator's judgment)	Study drug: May be reduced by one (1) tablet.  If, in the opinion of the Investigator, a Grade 2 AE has resolved to ≤ Grade 1, participant may resume study drug at the original dose.  If, in the opinion of the Investigator, the AE poses a significant safety concern such that a dose hold is considered, the Investigator should contact the Medical Monitor.				
Dose Interruption (Hold)					
Event	Recommended Action				
Grade ≥ 3 (NCI grading scale) AE deemed considered related to study drug by the Investigator AND  Precludes continued dosing at the current or at a reduced dose level due to safety concern or lack of tolerability in the Investigator's judgment	Study drug: Hold dose until ≤ Grade 2, then resume study drug at original dose. If, in the opinion of the Investigator, dosing should be resumed at a lower dose, contact the Medical Monitor for further discussion.  If the AE recurs or worsens, reduce dose by one tablet. Maximum dose hold is 5 continuous days. If, in the opinion of the Investigator, a longer dose hold is clinically needed, the Medical Monitor should be contacted for discussion.				
Drug Discontinuation	22				
Event	Recommended Action				
Grade ≥ 3 study drug-related AE that, at the discretion of the Investigator, warrants discontinuation of study drug (eg, has not improved or resolved after dose hold).	Study drug: Discontinue study drug. If the Investigator considers that the participant would benefit from continuing treatment, the Medical Monitor should be contacted.				

Abbreviations: AE, adverse event; SAE, serious adverse event.

All instances of voxelotor dose modification (dose reduction, interruption, or discontinuation) will be documented in the participant's medical record and study case report form (CRF). If the condition/event leading to the dose modification has resolved, the original dose level should be resumed, unless in the judgement of the Investigator this cannot be done safely.

Study personnel will review the EMR on a daily basis to ensure compliance or determine reasons for omission.

## 5.6 Prior and Concomitant Therapy

Prior medications taken within two days before study entry will be collected in CRF. Concomitant medications will be recorded through Study Day 7.

Fluconazole will be prohibited as a concomitant medication and has been listed as an exclusion criterion. The focus on fluconazole is due to its relatively common usage in our patients but we will also censor concomitant use of all moderate and strong CYP3A4 inhibitors in this early stage pilot study. Specifically, we will avoid the following concomitant medications:

- Moderate inhibitors of CYP3A4: amiodarone, erythromycin, fluconazole, miconazole, isavuconazole, diltiazem, verapamil, delavirdine, amprenavir, fosamprenavir, conivaptan.
- Strong inhibitors of CYP3A4: Clarithromycin, telithromycin, nefazodone, itraconazole, ketoconazole, voriconazole/posaconazole, atazanavir, darunavir, indinavir, lopinavir, nelfinavir, ritonavir, saquinavir, tipranavir.

Voxelotor is a weak 3A4 inhibitor so close monitoring of tacrolimus and/or cyclosprorine levels is needed if these drugs are concomitant medications. Daily levels are routine when used for inpatients.

There may also be risks, discomforts, drug interactions, or side effects that are not yet known.

# 5.7 Packaging

Voxelotor dispersible formulation will be dispensed. Voxelotor 100 mg and 300 mg dispersible tablets contain voxelotor drug substance along with formulation excipients. With the exception of artificial grape flavor, all excipients used in the dispersible tablets are listed in the FDA IID. The artificial grape flavor is listed under the Flavor and Extract Manufacturers Association (FEMA) guidelines and is considered a Generally Recognized as Safe (GRAS) material. All the excipients used in the formulation are either compendial per European Pharmacopoeia (Ph Eur) or are composed of mixtures that are compendial per Ph Eur or accepted by E number or European Commission regulation.

Voxelotor tablets (500 mg) will be packaged in high-density polyethylene (HDPE) bottles with induction sealed polypropylene (PP) child-resistant (CR) caps. As an alternate packaging, tablets may be supplied in multilaminate blisters.

## 5.8 Blinding of Study Drug

This is an open –label study and subjects will not be randomized. There is no blinding.

## 5.9 Receiving, Storage, Dispensing and Return

#### 5.9.1 Receipt of Drug Supplies

The initial shipment of voxelotor will be sent to Investigational Drug Services (IDS) Pharmacy once the site has met all requirements for activation by the Sponsor-Investigator and GBT. Initial quantity of study drug will be determined by study-specific forecasting criteria that includes, but not limited to the expected number of subject enrollment, treatment duration and dosing regimen.

Investigational Drug Services (IDS) Pharmacy will receive study drug shipped from sponsor. Upon receipt of the study treatment supplies, an inventory must be performed, and a drug receipt log filled out and signed by the person accepting the shipment. It is important that the designated study staff counts and verifies that the shipment contains all the items noted in the shipment inventory. Any damaged or unusable study drug in a given shipment (active drug or comparator) will be documented in the study files. The investigator must notify study sponsor of any damaged or unusable study treatments that were supplied to the investigator's site.

#### 5.9.2 Storage

#### **Storage and Handling Procedure**

All study medications will be stored in IDS pharmacy at controlled room temperature between 15°C to 25°C in the storage area of the investigational site pharmacy, which is a secure, temperature controlled, locked environment with restricted access. No special procedures for the safe handling of voxelotor drug products are required.

### 5.9.3 Dispensing of Study Drug

IDS pharmacy will maintain a Study Drug Dispensing Log. The following information will be recorded:

- Total amount of study drug dispensed (quantity of tablets dispensed)
- Identification (study number and initials) of the patient to whom the study drug was dispensed;
- Initials of the person who dispensed the study drug;
- Initials of the person who received the study drug for administration to the patient

## 5.9.4 Return or Destruction of Study Drug

The Investigator is responsible to ensure that all study drug is accurately accounted for. Any discrepancies must be described in writing. At the completion of the study, there will be a final reconciliation of drug shipped, drug consumed, and drug remaining. This reconciliation will be logged on the drug reconciliation form, signed and dated. Any discrepancies noted will be investigated, resolved, and documented prior to return or destruction of unused study drug. Drug destroyed on site will be documented in the study files. Any unused voxelotor will be returned to the Sponsor at the conclusion of the study or destroyed according to clinical site's SOP as mutually agreed upon by the Sponsor and the site.

# 6 Study Procedures

## 6.1 Screening (2 days before Voxelotor administration)

The following assessments will be performed during screening:

- Determine eligibility based on inclusion/exclusion criteria
- Obtain voluntarily given, written informed consent from subject or LAR
- Record demographics
- Record medical history
- Collect baseline physiological data for ESLD and ALI at rest and with exercise\*
  - $^{\circ}$  SpO2
  - ° FiO2
  - ° S/F ratio calculation
  - Heart rate
  - Modified Borg Dyspnea scale (MBDs) rating
- Collect additional baseline physiological data with ALI group
  - ° PaO2
  - ° SaO2
  - ° P/F ratio calculation
  - ° PaCO
  - ° A-a gradient calculation

## 6.2 -1 day before Voxelotor administration

The following assessments will be performed during Baseline:

- Collect baseline physiological data for ESLD and ALI at rest and with exercise\*
  - $^{\circ}$  SpO2
  - ° FiO2
  - ° S/F ratio calculation
  - Heart rate
  - MBDs rating
  - Collect additional baseline physiological data with ALI group
    - ° Pa02
    - ° SaO2
    - ° P/F ratio calculation
    - ° PaCO2
    - A-a gradient calculation
  - Blood sampling for central lab
    - ° Erythropoetin (5ml)
    - ° P50 (3ml)
    - PK (2ml)
  - Blood sampling for local lab
    - o Pregnancy test for women of childbearing potential if not done as SOC (2ml)
    - o CBC (3ml)
    - o CMP (4.5ml)

# 6.3 Day 1

- Blood sampling for central lab
  - P50 (3ml)
  - ° PK (2ml)
- Blood sampling for local lab
  - ° CBC (3ml)
  - ° BMP (4.5ml)
- Administer 500 mg Volexotor twice daily (or up to three times a day if patient tolerates initial dose per PI)
- Collect daily physiological data for ESLD and ALI at rest and with exercise\*
  - $^{\circ}$  SpO2
  - ° FiO2
  - ° S/F ratio calculation
  - ° Heart rate
  - MBDs rating
- Collect additional daily physiological data with ALI group
  - ° PaO2
  - ° SaO2
  - ° P/F ratio calculation
  - ° PaCO2
  - A-a gradient calculation
- Record adverse events

## 6.4 Day 2

- Blood sampling for central lab
  - P50 (3ml)
  - ° PK (2ml)
  - ° Erythropoietin (5ml)
- Blood sampling for local lab
  - ° CBC (3ml)
  - ° BMP (4.5ml)
- Administer 500 mg Volexotor twice daily (or up to three times a day if patient tolerates initial dose per PI)
- Collect daily physiological data for ESLD and ALI at rest and with exercise\*
  - $^{\circ}$  SpO2
  - ° FiO2
  - ° S/F ratio calculation
  - Heart rate
  - MBDs rating
- Collect additional daily physiological data with ALI group
  - $^{\circ}$  PaO2
  - $\circ$  SaO2
  - P/F ratio calculation

- ° PaCO2
- ° A-a gradient calculation
- Record adverse events

### 6.5 Day 3-5

- Blood sampling for central lab
  - P50 (3ml)
  - PK (2ml)
- Blood sampling for local lab
  - ° CBC (3ml)
  - BMP (4.5ml)
- Administer 500 mg Volexotor twice daily (or up to three times a day if patient tolerates initial dose per PI)
- Collect daily physiological data for ESLD and ALI at rest and with exercise\*
  - $^{\circ}$  SpO2
  - ° FiO2
  - ° S/F ratio calculation
  - Heart rate
  - MBDs rating
- Collect additional daily physiological data with ALI group
  - ° PaO2
  - ° SaO2
  - ° P/F ratio calculation
  - ° PaCO2
  - A-a gradient calculation
- Record adverse events

# 6.6 Day 6 (Wash out period)

- Collect daily physiological data for ESLD and ALI at rest and with exercise\*
  - $^{\circ}$  SpO2
  - ° FiO2
  - ° S/F ratio calculation
  - ° Heart rate
  - MBDs rating
- Collect additional daily physiological data with ALI group
  - ° PaO2
  - ° SaO2
  - ° P/F ratio calculation
  - ° PaCO2
  - A-a gradient calculation
- Blood sampling for central lab
  - PK (2ml)
  - ° P50 (3ml)
  - ° Erythropoetin (5ml)

- Blood sampling for local lab
  - ° CBC (3ml)
  - ° BMP (4.5ml)
- Record adverse event

## 6.7 Day 7 (Wash out period)

- Collect daily physiological data for ESLD and ALI at rest and with exercise\*
  - ° SpO2
  - ° FiO2
  - S/F ratio calculation
  - ° Heart rate
  - ° MBDs rating
- Collect additional daily physiological data with ALI group
  - ° PaO2
  - ° SaO2
  - ° P/F ratio calculation
  - ° PaCO2
  - A-a gradient calculation
- Blood sampling for central lab
  - ° PK (2ml)
  - ° P50 (3ml)
- Blood sampling for local lab
  - ° CBC (3ml)
  - ° CMP (4.5ml)
- Record adverse event

#### 7 \* Statistical Plan

# 7.1 Sample Size Determination

This is a pilot study and will be used to determine effect size for future prospective study

#### 7.2 Statistical Methods

Descriptive statistics for patient characteristics and baseline factors will be presented as median and interquartile range for continuous variables and number and percentage for categorical variables. The primary outcome will be change in S/F ratio from baseline to 2 days after initiation of voxelotor treatment, and the secondary outcome will be change in S/F ratio from baseline to 5 days after initiation of voxelotor treatment. Each will be compared using the Wilcoxon Signed Rank test. The baseline value will be defined as the median S/F ratio measurement during the 48-hour period before initiation of voxelotor treatment. Similarly, the

\*only if feasible/ ambulatory patients only. Exercise protocol is SOC and data collected will be reviewed from medical record.

day 2 and day 5 S/F ratio values will be defined as the median S/F ratio measurement on the second and fifth days after initiation of treatment.

All S/F ratio values will also be analyzed using a mixed-effects model with a random intercept for each patient and time in hours (relative to initiation of voxelotor treatment) as a fixed effect. Quadratic and cubic terms for time will also be included to allow for flexible modeling of treatment effect over time. We will tabulate and report all observed adverse events occurring during this trial.

For the ALI group with an arterial line in place, the PaO2/FiO2 (P/F) ratio will also be compared in a similar manner to identify whether any improvement in S/F ratio is due to clinical improvement of ALI, as reflected in the P/F ratio. The concept of Voxelotor use is an improvement in the S/F ratio (the result of left-shift in p50) for a given P/F ratio (the result of pulmonary function limiting PaO2). This may be especially important for the ALI sub-study cohort, as ALI could improve during the 5 day dosing period. Realistically, however, such progress is typically slow and, in contrast, the end-stage lung disease cohort would not be expected to improve and S/F ratio alone would reflect voxelotor effect without the need to track P/F ratios.

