#### Central lab collection and processing:

PK, P50, and erythropoetin labs will be collected, processed, and stored as described in Study Lab Manual.

**Voxelotor administration**: The day after obtaining written, informed consent, 500 mg of voxelotor will be administered two times a day (for a total daily dose of 1000 mg per day) for 5 days. This dose may increase to a total maximum daily dose of 1500 mg (500 mg three times a day) if subject tolerates initial dose as determined by Principal Investigator (PI). Subjects will be dosed orally with approved tablets or recently approved dispersible tablet in water and given via feeding tube (when indicated). In the event the voxelotor administration needs to be modified during one of the study administration days for patient safety reasons, the PI will follow the dose modification guidelines for study related adverse events (Table 4). If the PI determines discontinuation of voxeletor is necessary for patient safety, then the protocol will progress to the wash out phase identified in the Schedule of Activities table 2.

If a patient on the lung transplant list receives an "initiation call" from the lung transplant coordinators, study medication will be held until a determination is made to proceed with solid organ transplantation. In the event the study patient does not receive the solid organ transplant, study medication administration will be resumed as previously scheduled and missed doses will be not be considered protocol deviations as the PK and pharmacodynamics (PD) of Voxelotor in the setting of surgery, blood loss, and blood transfusion is unknown. In the event the study patient receives a "go call" for solid organ lung transplant then study medication will be discontinued and the subject will proceed to the study wash out phase.

Voxelotor is oral administration only and the effect of blood transfusion "diluting" the Voxelotor modified RBCs is unknown, so the effect of Voxelotor in this setting will be confounded by the common scenario of blood transfusion and/or hemodilution and they will enter the wash-out period. Also, the indication for Voxelotor, to maintain SaO2 in the face of a significant Alveolar-arterial pO2 gradient, will have passed with the implantation of donor lungs.

Study completion is at the end of 2 day wash out period defined by 2 days after the last administration of Voxelotor.

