# 4 Subject Selection and Withdrawal

#### 4.1 Inclusion Criteria

- 1. Oxygen dependency due to an end-stage lung disease (pre-lung transplant population) or ALI/acute lung injury (for example but not limited to primary allograft dysfunction, infectious pneumonia, aspiration, non-cardiogenic pulmonary edema). ALI will be defined as per Berlin criteria with a P/F ratio < 100 denoting severe acute respiratory distress syndrome (ARDS), < 200 denoting moderate and < 300 mild ARDS. ALI and mild ARDS are considered synonymous. In the event of inability to obtain arterial blood gas analysis to calculate a P/F ratio, we will consider a range of patients requiring standard nasal cannulae flowing at 6 LPM (liters per minute) to maintain SaO2 > 90% as ALI, and Salter High -Flow nasal cannulae at 12-15 LPM in order to maintain SaO2 > 85% as severe ARDS.
- 2. At least 48 hours of stable, increased oxygen requirement or ventilatory support prior to the start of drug administration if consented.

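### The supportive mixed model has only a patient random intercept, so its standard errors for change in S/F over time are too small if patient trends vary or readings are autocorrelated

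*Combined protocol and SAP*

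**What the plan says.** Section 7.2 has two layers of analysis. The changes in S/F from the 48-hour pre-dose baseline to Day 2 (primary) and Day 5 (secondary) are tested first: "Each will be compared using the Wilcoxon Signed Rank test". All S/F values then enter a "mixed-effects model with a random intercept for each patient and time in hours (relative to initiation of voxelotor treatment) as a fixed effect". On the mean curve it adds: "Quadratic and cubic terms for time will also be included to allow for flexible modeling of treatment effect over time".

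No random slope, serial-correlation structure, robust variance or cohort term is stated. Nor is it stated which contrast, interval or p-value will be reported from the model.

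On trends, Section 7.2 allows for recovery in acute lung injury (ALI), "as ALI could improve during the 5 day dosing period", then tempers this: "Realistically, however, such progress is typically slow". It does not expect the end-stage lung disease (ESLD) cohort to improve. Section 4.1 admits either disease ("Oxygen dependency due to an end-stage lung disease (pre-lung transplant population) or ALI/acute lung injury") and sets no quota. Table 2 schedules S/F on nine study days, D-2 to D7.

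**The concern.** A random intercept removes differences in level between patients and nothing else. What is left is treated as independent noise around one shared curve. Two ordinary features of such data break that assumption: some patients improve or worsen faster than others, and readings close in time resemble each other. In either case the model counts each patient's repeated readings as more independent information about change than they carry.

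This is the only planned analysis that uses every S/F value, and Section 7.2 presents it as a description of treatment effect over time. An interval or p-value from it could make a 20-patient pilot look more precise than it is.

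**Working it through.** The plan states no power, variance or precision figure, so there is nothing to reproduce.

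**Inputs from the documents.** n = 20; nine study days; baseline D-2 and D-1; cubic time; patient random intercept.

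**Assumed inputs.** Intercept SD 40 and residual SD 25 in S/F units; linear trends and no drug effect; at first one reading per day, equally spaced; a two-sided 95% interval. The contrast is the fitted Day-2 or Day-5 value minus the mean of fitted D-2 and D-1, chosen because these are the endpoint times. Error is the chance that the interval misses the true mean change.

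**Closed form.** Set D1 as t = 0 in days, so D-2 is -2, Day 2 is 1 and Day 5 is 4. The contrast is a weighted sum of the nine daily means with weights w. The weights sum to zero, so the intercept cancels.
- w'w = 0.6914 (Day 2) and 0.8299 (Day 5).
- w't = 1 + 1.5 = 2.5 (Day 2) and 4 + 1.5 = 5.5 (Day 5).
- Model variance = (residual mean square) × w'w / 20.
- True variance with slope SD b = (625 × w'w + b² × (w't)²) / 20.

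For b = 5, unmodelled slopes raise the residual mean square to 625 + 25 × (20 × 60 − 60)/157 = 806.5, where 60 is the sum of squared deviations of the nine times and 157 the residual df.
- Day 5: model SE = √(806.5 × 0.8299/20) = 5.79; true SE = √((518.7 + 756.3)/20) = 7.98. Ratio 0.725; error about 2 × [1 − Φ(1.975 × 0.725)] = 15.2%.
- Day 2: model SE 5.28; true SE √((432.1 + 156.3)/20) = 5.42. Ratio 0.974; error about 5.4%.

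For AR(1) 0.5 the true variance is w'Σw/20, with covariance 625 × 0.5 to the power of the lag in days. At Day 5 the model SE is 4.54 against a true 6.67, so error is about 17.9%.

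**Simulation** (20,000 trials per setting):

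| Setting | Day 2 error | Day 5 error |
|---|---|---|
| Model assumptions hold | 5.0% | 5.0% |
| Slope SD 2 / 5 / 10 per day | 4.8 / 5.6 / 6.9% | 7.1 / 15.5 / 27.0% |
| AR(1) 0.3 / 0.5 / 0.7 | 8.4 / 10.1 / 11.2% | 12.4 / 18.5 / 24.0% |

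Patient-clustered t intervals (19 df) give 4.7% to 5.3% in these slope and AR(1) settings.

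**Check with REML fits of the planned model** (2,000 trials), Day-5 error, model against CR2-clustered: 5.0% against 4.6% when assumptions hold; 15.0% against 4.7% (slope SD 5); 19.2% against 6.0% (AR(1) 0.5). Section 3.1 says "Study completion is at the end of 2 day wash out period defined by 2 days after the last administration of Voxelotor", so early stopping shortens follow-up. With an assumed 30% stopping after Day 1 to 4, the last two pairs become 15.0% against 4.6% and 17.4% against 5.2%.

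**Sensitivity to the assumptions.**
- Residual SD 15 to 40: Day-5 error 24.1% down to 9.5% (slope SD 5), and 18.4% to 17.9% (AR(1) 0.5).
- Slopes that diverge only after dosing, SD 5: Day-5 error about 11%, with no inflation at Day 2.
- Change measured from the fitted value at 0 h, AR(1) 0.5: about 15% at both days.
- Three readings per day, slope SD 5: about 9% (Day 2) and 32% (Day 5). With correlation 0.5 per day: about 30% to 33% and 41% to 44%.
- Cohort trends differing by 4 per day: Day-5 error 7.2% if the ALI/ESLD mix is random at 50/50, but 4.6% if it is fixed at 10/10.

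**Mean curve.** If an assumed drug effect is absent before dosing, full on D1 to D5 and gone on D6 and D7, the fitted cubic recovers 87% of the true Day-2 change and 64% of the Day-5 change, even in balanced data.

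**The case against.** The strongest reply is that the plan promises no interval or p-value from this model, tests its endpoints by other means, and supplies none of the variances behind the figures above. All of that stands. The point therefore applies to inference that might be taken from the model, and its size is assumed.

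Five stronger readings are tempting and are not supported:
- **That the primary and secondary tests are compromised.** The Wilcoxon tests use one change per patient, so within-patient covariance does not enter.
- **That the problem sits mainly at Day 5.** This follows from the 48-hour-baseline contrast and one reading per day. From a 0 h reference the two days are about equal. Section 7.2 takes daily medians and measures time in hours, which suggests several readings per day, though no count is given. Day 2 is then also clearly affected.
- **That differing ALI and ESLD trends alone make the intervals too narrow.** This holds only if inference is to a wider population with an unfixed mix, which the plan does not define. For a fixed mix the intervals are not too narrow, although the pooled curve then describes neither cohort.
- **That the point estimate is safe.** That is true of covariance misspecification in balanced data. It does not extend to a cubic that fits an on/off drug course poorly.
- **That the future study's effect size will come from this model.** Section 7.1 says only: "This is a pilot study and will be used to determine effect size for future prospective study". It names no source.

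It is also fair that Section 4.1 requires 48 hours of stable oxygen need before dosing, so slopes starting at D-2 may be too severe. Starting them at dosing lowers the Day-5 figure for slope SD 5 from 15.5% to about 11%, still above 5%.

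**Conclusion.** The concern holds in conditional form. If patient trends vary or readings are autocorrelated, standard errors for change over time from the planned model are too small. If neither holds and the cubic fits, they are right.

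Under the assumed inputs, Day-5 error runs from about 7% (slope SD 2) to 27% (slope SD 10), and from about 12% to 24% for AR(1) 0.3 to 0.7. More readings per day make it worse and bring in Day 2. None of these sizes can be fixed from the documents.

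This is a modest point about a supportive analysis. It is worth acting on because the remedy is cheap.

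**What to change.** Keep the cubic, random-intercept model. State in Section 7.2 that any standard errors, intervals or p-values reported from it for the baseline-to-Day-2 and baseline-to-Day-5 changes use patient-clustered standard errors with a small-sample correction (for example CR2) and a t reference. Random slopes or AR(1) residuals can be optional sensitivity analyses. Show the changes by cohort descriptively, with intervals and without tests.

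**Cost.** SAP wording only.
- If the planned model is right, the Day-5 interval widens by about 5% (21.0 against 20.1 S/F units).
- With slope SD 5 it widens by about 45% (33.0 against 22.8), which is the honest width.
- If cohorts differ and the mix is fixed, clustered intervals are conservative: Day-5 error 3.0% at a difference of 4 per day and 0.2% at 10 per day.
- By-cohort intervals will be wide: 31.7 to 49.7 with 10 patients in a cohort and 53.2 to 83.7 with 5, for slope SD 0 to 5.

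Clustering does not repair a cubic that misses the on/off-drug time course. Any statement that the point estimate is unaffected should be limited to covariance misspecification.
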